1.0 Objectives / Specific Aims

This study will examine racial differences in stress responses between African American and white male smokers as part of the Translational Research Center in Lung Cancer Disparities (TRACER).

- **Aim 1: Examine racial differences in acute physiological stress responses between African American and white male smokers using a laboratory model. The association between acute physiological stress response and tobacco-related behaviors will also be evaluated.**

Hypotheses: African American smokers will be more likely than white smokers to have a blunted cortisol response to an acute laboratory stressor. African American smokers will also have significantly greater cigarette craving and be more likely to smoke following exposure to an acute physiological stressor compared to white smokers following an acute laboratory stressor.

- **Aim 2: Evaluate racial differences in daily cortisol patterns between African American and white male smokers.**

Hypotheses: African American smokers will be more likely than white smokers to have blunted daily diurnal cortisol slopes. Compared to white smokers, African American smokers will have lower absolute cortisol values during the waking day.

- **Aim 3: Identify factors that are important to acute and daily stress responses among African American and white male smokers by examining acute and daily cortisol patterns based on exposure to chronic stressors.**

Hypotheses: Acute and daily cortisol responses will be associated with chronic stressors such that men who have greater exposure to SES, structural, and psychosocial stressors will have blunted acute and daily cortisol patterns. The relationship between acute and daily cortisol patterns, nicotine metabolism, and nicotine dependence will also be explored among African American and white male smokers as part of this aim.

- **Aim 4: Examine social and clinical factors associated with study enrollment and retention.**

Hypotheses: Those with greater comorbidities and social issues (i.e. lower SES, education, social support) will have lower rates of study enrollment and retention compared to those with fewer comorbidities and social issues.

2.0 Background

Cigarette smoking is a leading cause of morbidity and mortality from lung cancer among adults in the US; smoking cessation is the best preventive strategy for reducing lung cancer risk and addressing racial disparities in outcomes. Despite this, many smokers are unwilling or unable to make a quit attempt, and among those who try to quit smoking, utilization of evidence-based treatment is poor, especially in racial minorities. Stress relief, and the avoidance of adverse psychological and physiological reactions, are among the primary reasons for smoking initiation, maintenance, and relapse in all populations. Stress responses have both psychological and physiological consequences that are important to smoking behaviors and cessation outcomes, and racial differences in physiological stress responses have not been examined between African American and white smokers.

Physiological stress responses are among the multilevel determinants of cancer health disparities that need to be examined within the context of other SES, psychosocial, and structural factors. This study will be the first to examine racial differences in stress responses between African American and white male smokers at increased risk for lung cancer morbidity and mortality by measuring acute cortisol responses to a laboratory stressor and evaluating racial disparities in daily cortisol patterns among these men in their

neighborhoods and communities. Together with contextualized data on acute and chronic stress responses based on SES, psychosocial, and structural factors, this study will generate novel empirical data that can be leveraged into precision strategies for lung cancer prevention through smoking cessation and other intervention approaches.

3.0 Study Setting

This study will be conducted at MUSC Health. Participants will be identified using electronic health records (EHR) and will participate in laboratory visits at the Research Nexus Laboratory in the Clinical Sciences Building at MUSC to measure acute stress responses. All baseline and follow-up assessments will be conducted by telephone or online using a redcap weblink. *This study is being conducted as part of the Translational Research Center in Lung Cancer Disparities (TRACER) that includes: MUSC, the Massey Cancer Center at the Virginia Commonwealth University (VCU), and the City of Hope Comprehensive Cancer Center (COH).*

4.0 Inclusion and Exclusion Criteria/ Study Population

Primary care patients at MUSC Health will be identified using EHR and those who meet inclusion criteria will be contacted by telephone to complete a screening interview and baseline assessment that measures socioeconomic stressors and other variables. To be eligible to participate in the study, the following criteria will be applied.

Inclusion Criteria

- African American and white males
- Between the ages of 18-75 years old
- Smoke at least 5 to 10 cigarettes per day

Exclusion Criteria

- Smokers who have a serious cognitive disorder or psychiatric illness
- Have a personal history of lung cancer
- Personal history of usage of illicit drug and alcohol abuse
- Enrollment in a smoking cessation treatment program during the past 6-months
- Current use of a nicotine replacement therapy
- Have any positive response on the Mini International Neuropsychiatric Interview (MINI) screener

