6.0 Recruitment Methods

Two recruitment strategies will be used to identify smokers to participate in the study. First, the initial recruitment strategy will be identifying patients by searching EHRs using smoking status and ICD-10 diagnosis codes (e.g., smoking status, psychiatric illness, cognitive disorders) to identify smokers who are potentially eligible to participate in the study. Additionally, text algorithms will be applied to chart notes to help supplement the EHR search because smoking behaviors may be under-reported. Following identification and application of exclusion criteria to the EHR, a patient list of individuals who are identified as current smokers and meeting other eligibility criteria will be created and provided to the investigative team. These patients will be mailed an invitation letter that describes the purpose of the study and the procedures involved in participation. The letter will also include a local number and email address to respond if they are not interested in being contacted for study participation. Those who do not opt out of

participation will be contacted for the baseline and screening telephone interview. The South Carolina Translational Research Center (SCTR) will conduct the EHR search and generate patient lists. Second, a community-based approach in which smokers self-refer for participation from newspaper, radio advertisements, and social media will be used to recruit study participants. For individuals who self-refer for study participation, the screening interview and baseline survey will be completed to determine eligibility and complete enrollment procedures. Marketing materials will be developed using a evidence-based community engagement strategies. Project investigators will consult with members of the community engagement core to develop materials that are tailored and appropriate. Once these materials are developed they will be submitted to the IRB for review and approval.

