7.0 Consent Process

This study will use the procedures described below to obtain informed consent for study participation.

Electronic Health Record Data Abstraction. A full waiver of HIPAA Authorization is requested to generate the EHR query that will be used to establish the list of patients who are potentially eligible to participate in the study and to obtain other personal health identifiers (e.g., MRN, names, address, telephone numbers) for sending invitation letters and conducting recruitment calls. The waiver of HIPAA Authorization will also include permission to abstract clinical (e.g., co-morbidities, medications, vital signs) and socioeconomic data (e.g. insurance type, race/ethnicity), and to utilize text algorithms developed by BMIC to abstract information from clinical notes relating to smoking status. Clinical and sociodemographic data abstracted from the EHR will be included in de-identified datasets for analysis of study outcomes relating to factors (i.e. zipcode, co-morbidities) associated with smoking behaviors, stress responses, and enrollment and retention . The outcomes rendered from the EHR data that is obtained will help to inform future studies that further address disparities relating to lung cancer risk.

All PHI data will be collected at the time of screening. No further data collection occurs on these participants following screening and EHR abstraction under the full waiver. Further data collection for participants who choose to enroll will be covered under the partial waiver for the baseline interview, and the signed informed consent form and HIPAA if they choose to participate further in the study.

Screening Interview and Baseline Survey. A waiver of written informed consent/partial waiver of signature element is requested to complete the screening interview and baseline survey. Patients will be read a statement of study information before obtaining verbal consent. Once verbal consent is achieved, the screening interview will be completed by telephone. Baseline surveys will be completed according to the participant's preference either by telephone or through self-administration via a redcap survey weblink.

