Pre-Challenge Visit. Following completion of the screening interview and baseline survey, participants will complete a pre-challenge visit to obtain urine samples that will be used to determine final eligibility. The pre-challenge visit will be completed at the Research Nexus Lab at MUSC. Participants will be asked to smoke as usual prior to the pre-challenge visit but to not eat or drink one hour before the session. During the Pre-Challenge Visit, screening tests will determine final eligibility, these include urine toxicology; individuals whose results indicate current substance abuse (e.g., cocaine) will be excluded (not eligible for further participation). Saliva samples will also be obtained during the pre-challenge visit to determine cortisol and cotinine levels using established salivary swab collection methods and validated thresholds. To further evaluate and confirm active smoking behaviors, a breath monitor will be used to measure levels of carbon monoxide in the blood. The MINI International Neuropsychiatric Interview (MINI) will be administered by a trained research technician to evaluate mental status and psychiatry exclusion criteria. Participants will be excluded from participation in the laboratory stress visit if they meet the exclusion criteria (e.g., positive responses on the MINI, or positive toxicology result). Participants eligible following pre-challenge visit will be scheduled for the stress exposure visit described below.

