To examine the effects of race on acute stress responses to the TSST laboratory stressor the response area under the curve (rAUC) for cortisol will be calculated using trapezoidal approximation with the samples obtained at time zero (T0) to the last measurement (T24m). Analysis will adjust for baseline cortisol levels by subtracting the rectangle defined the baseline sample and total observation time (T24min) from the total area under the curve, thus, it is possible to have negative rAUC values if cortisol levels decline below baseline.⁹¹ A generalized linear regression model will be conducted with rAUC as the dependent variable and race (AA/Black, white) as the between-subjects factor. The effects of nicotine metabolism rates, nicotine dependence, and cigarettes smoked per day will be examined in analysis of covariance that include rAUC as the dependent variable and race as the between-subjects variable. The extent to which cortisol changes are blunted will be determined by calculating the difference between the first and last cortisol assessment during the TSST.⁹⁰ Cortisol values that do not change over time or those that are closer to zero will be considered blunted.³⁰ Similar regression models will be used to test for racial differences in cortisol levels at each timepoint following exposure to an acute laboratory stressor, the proportion who smoke after the TSST, and scores for cigarette craving. A random effect will be added to the statistical models to allow for differences in participants recruited from different sites (MUSC and VCU). Models will be adjusted for known and potential confounders (e.g., nicotine metabolism rates).

Aim 2. Evaluate racial differences in *daily* cortisol patterns between AA/Black and white male smokers. *Hypotheses:* AA/Black smokers will be more likely than white smokers to have blunted daily DCS. Compared to white smokers, AA/Black smokers will have lower absolute cortisol values during the waking day. This aim will examine racial disparities in cortisol responses between AA/Black and white male smokers in their neighborhood and community settings at 4- and 8-weeks after the TSST has been completed. Changes in cortisol levels will be the primary outcome variable and will be measured at multiple critical timepoints during the waking day.

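### Cortisol is the outcome of Aims 1 to 3, but the plan neither excludes glucocorticoid users nor asks about use on collection days, so drug-suppressed cortisol can be scored as a blunted response

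*Combined protocol and SAP*

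**What the plan says.** Section 4.0 lists one medicine among its exclusions: "Current use of a nicotine replacement therapy". The other drug-related criterion concerns substances rather than medicines: "Personal history of usage of illicit drug and alcohol abuse". Men are admitted over a wide age range ("Between the ages of 18-75 years old").

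Section 8.0 describes each later point at which a medicine could be noticed:
- The baseline survey covers sociodemographics, stressors and smoking.
- The pre-challenge visit adds carbon monoxide, cotinine, the MINI and urine toxicology, where "individuals whose results indicate current substance abuse (e.g., cocaine) will be excluded".
- The TSST visit records cigarettes smoked beforehand.
- The home instructions cover food, drink, toothbrushing, exercise and alcohol.
- The collection log covers times, cigarettes, quit attempts, stress and life events.

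None of these descriptions mentions a glucocorticoid or any other cortisol-altering medicine.

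Two provisions bear on medicines indirectly. Section 7.0 seeks "permission to abstract clinical (e.g., co-morbidities, medications, vital signs" and similar items from the EHR, for analyses that include stress responses. Section 10.1 adjusts the models for confounders that it leaves open, giving nicotine metabolism as its example. It also examines nicotine dependence and cigarettes per day as covariates.

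Section 6.0 has a second recruitment route, "a community-based approach in which smokers self-refer for participation from newspaper, radio advertisements, and social media". For these men, eligibility rests on the screening interview and baseline survey.

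Section 10.1, under the Aim 1 analysis, takes the first-to-last cortisol difference during the TSST and states: "Cortisol values that do not change over time or those that are closer to zero will be considered blunted". Aim 2 defines blunting in a similar way.

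**The concern.** A glucocorticoid acts directly on the quantity being measured. A man whose cortisol is held low and flat by a medicine has a first-to-last difference near zero and a baseline-corrected area under the curve near zero. Under the plan's rule he counts as blunted, and nothing in the rule separates him from a man whose response is blunted for the reasons the study wants to examine.

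What follows depends on how use is distributed:
- **Equal use in both racial groups.** The planned difference shrinks and power falls, but no false racial difference appears.
- **Use that differs by race.** Part of the Aim 1 or Aim 2 contrast becomes a drug effect, which can inflate or hide a difference according to which group uses more.
- **Use that tracks SES, psychosocial or structural stressors.** Aim 3 can show a stressor association that the medicine produced, or miss a real one.

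Exposure on a collection day that nobody records may not be recoverable afterwards.

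**Working it through.** **Inputs from section 10.1, Aim 1.** 50 men per group; mean DCS 0.20 (SD 0.20) in African American men and 0.35 (SD 0.30) in white men; difference 0.15 μg/dL; two-sided alpha 0.05; stated power 84%.

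**Reproducing the stated power.** Standard error = √((0.20² + 0.30²)/50) = √(0.13/50) = 0.0510. Non-centrality = 0.15/0.0510 = 2.94. Power is 83.7% by normal approximation and 82.9% by Welch t-test. The stated 84% is reproduced. The Welch figure is the reference below.

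**Assumptions not in the documents.** A share p of a group uses a glucocorticoid. Users have mean change 0 and SD 0.05 (full suppression). Non-users follow the planned mean m and SD s. The documents give no prevalence, so a range is shown.

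**Formulas.** Group mean m′ = (1 − p)m. Group variance = (1 − p)(s² + m²) + p(0.05²) − m′². Welch power is then recomputed at 50 per group.

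**Example, 10% use in both groups.**
- African American: m′ = 0.9 × 0.20 = 0.18; variance = 0.9(0.04 + 0.04) + 0.1(0.0025) − 0.0324 = 0.03985.
- White: m′ = 0.9 × 0.35 = 0.315; variance = 0.9(0.09 + 0.1225) + 0.1(0.0025) − 0.099225 = 0.092275.
- Difference 0.135; standard error √((0.03985 + 0.092275)/50) = 0.0514; non-centrality 2.63; power 73.8%.

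**Planned difference true:**

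| Use, African American / white | Difference | Power |
|---|---|---|
| 0% / 0% | 0.150 | 82.9% |
| 2% / 2% | 0.147 | 81.1% |
| 5% / 5% | 0.1425 | 78.5% |
| 10% / 10% | 0.135 | 73.8% |
| 20% / 20% | 0.120 | 64.0% |
| 5% / 15% | 0.1075 | 54.2% |
| 15% / 5% | 0.1625 | 88.1% |

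**No true difference (both groups 0.35, SD 0.30).** With equal use the false difference is 0 and the rejection rate stays at 5%. With 15% use in African American men and 5% in white men, the false difference is 0.35 × (0.95 − 0.85) = 0.035. That is 0.035/0.15 = 23% of the target, and the two-sided rejection rate is 8.8%.

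**Weaker suppression.** If users keep half the mean change with unchanged SD, equal use of 10% gives 77.8% power and 20% gives 72.4%.

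**The case against.** The strongest reply is that the plan is not blind to medicines. Section 7.0 abstracts medications and comorbidities from the EHR and names stress responses among the outcomes they will serve. Section 9.1 links EHR clinical data to cortisol results. Section 10.1 compares enrollees with decliners on clinical factors to choose control variables, and leaves its confounder list open. The screening and baseline instruments are not reproduced in the documents, so they may contain a medication question. All of this stands, and a reader who infers that the plan ignores medicines altogether goes too far.

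It does not close the gap. No provision mentions glucocorticoids or ties medication data to eligibility or to a cortisol model. Comparing enrollees with decliners detects selection into the study, not drug effects on cortisol. EHR data are not assured for self-referred men. A reader might also infer that section 7.0 forbids later medication data. It does not: the bar on further collection applies under the full waiver, and collection from enrolled men is covered separately. A later check is simply not specified.

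A second tempting inference is that an observed racial or stressor difference would be a drug artefact. The documents do not support that: it needs use that differs by race or stressor exposure, and they give no data on use in either group. If white men used more, the bias would run against the study's hypothesis.

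The reply is also right about the figures. The prevalences are assumed, and full suppression is a strong assumption for inhaled, nasal or topical products. The planning figures are for DCS, whereas the Aim 1 race model uses the response area under the curve, for which no mean or SD is given.

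**Conclusion.** The concern holds in this form: followed as written, the plan can enrol men with drug-suppressed cortisol and class them as blunted, and it commits to no step that would identify or handle them. With equal use the consequence is dilution and lost power; bias in either direction requires unequal use.

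The size is illustrative only. Under full suppression, equal use of 2% costs about 2 points of power and leaves it above 80%, while 5% takes it below 80%. Unequal use moves power from 54.2% to 88.1% across the two opposite 5%/15% splits. With no true difference, the 15%/5% split raises rejection from 5% to 8.8%. These figures rest on assumed prevalences and on the DCS planning values, and do not transfer directly to the modelled area under the curve. The gap in the text does not depend on them. It is a real and cheaply removed threat to validity and power, not one that defeats the study.

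**What to change.** 1. Ask every man about current glucocorticoid use (systemic, inhaled, nasal, topical) in the screening interview, for both recruitment routes. Repeat the question on the TSST visit record and on the week 4 and week 8 logs.
2. Add current systemic glucocorticoid use at screening to the section 4.0 exclusions, as a study-eligibility criterion.
3. State in section 10.1 that collection days under systemic use begun after screening are left out of the main cortisol analyses.
4. Pre-specify a repeat of the race and stressor models without men flagged for inhaled, nasal or topical use.
5. Report the numbers of men and collection days excluded, by race.

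No medicine is to be changed or withheld for the study.

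The cost is one eligibility line, one question on existing forms and one sensitivity analysis. Some screened men and collection days will be lost, possibly more among men with comorbidity, whom Aims 3 and 4 also study. Reporting exclusions by race lets readers judge that trade-off.

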5.0 Number of Subjects

The study will enroll 100 African American (n=50) and white (n=50) male smokers.

6.0 Recruitment Methods

Two recruitment strategies will be used to identify smokers to participate in the study. First, the initial recruitment strategy will be identifying patients by searching EHRs using smoking status and ICD-10 diagnosis codes (e.g., smoking status, psychiatric illness, cognitive disorders) to identify smokers who are potentially eligible to participate in the study. Additionally, text algorithms will be applied to chart notes to help supplement the EHR search because smoking behaviors may be under-reported. Following identification and application of exclusion criteria to the EHR, a patient list of individuals who are identified as current smokers and meeting other eligibility criteria will be created and provided to the investigative team. These patients will be mailed an invitation letter that describes the purpose of the study and the procedures involved in participation. The letter will also include a local number and email address to respond if they are not interested in being contacted for study participation. Those who do not opt out of

participation will be contacted for the baseline and screening telephone interview. The South Carolina Translational Research Center (SCTR) will conduct the EHR search and generate patient lists. Second, a community-based approach in which smokers self-refer for participation from newspaper, radio advertisements, and social media will be used to recruit study participants. For individuals who self-refer for study participation, the screening interview and baseline survey will be completed to determine eligibility and complete enrollment procedures. Marketing materials will be developed using a evidence-based community engagement strategies. Project investigators will consult with members of the community engagement core to develop materials that are tailored and appropriate. Once these materials are developed they will be submitted to the IRB for review and approval.

